### **5.3 Packaging, Labeling and Storage**

The study drug (active and placebo) will be packaged and labeled by CREAPHARM (Bordeaux, France) in accordance with applicable local regulatory requirements. One Viaskin® patch will be placed per pouch and each pouch will be labeled. The labeled pouches will be placed in labeled treatment boxes to be dispensed to subjects at each visit, with enough quantity of Viaskin® patches to cover the period between 2 consecutive visits.

The labeled and packaged study drug must be stored in accordance with the Sponsor's instructions (in the monitored refrigerator between 2°C and 8°C [35.6°F to 46.4°F]). Shipments from depots to clinical sites will be performed at refrigerated temperature between 2°C to 8°C [35.6°F to 46.4°F] with a temperature monitoring device. Storage at

ambient temperature for short and/or intermittent periods of time, including transportation from the clinical site to the subject's home, is permitted.

Upon receipt of a shipment request via IWRS, the study drug will be shipped to the clinical site. The site pharmacist or any other staff member designated for this task will receive and store the study drug until the time of dispensing it to the Investigators. Until dispensed by the Investigator to the subjects, the study drug will be stored in a securely locked area, accessible to authorized personnel only. At the end of the study, or at times designated by the Sponsor, and after complete accountability, the site pharmacist or the designated person will be responsible for preparing the return of the unused study drug to the study drug distributor. Destruction of study drug on-site should be avoided. However, in some cases, and upon authorization from the Sponsor, destroying the unused study drug on-site, with provision of a corresponding certificate of destruction, may be allowed.

#### 5.4 Blinding and Breaking the Blind

The study will be performed in a double-blind manner. Active and placebo Viaskin® patches will be supplied in identical pouches and will be similar in physical appearance, thereby enabling double-blind conditions.

The treatment codes will be held according to the IWRS. Further instructions for emergency code break will be provided in a separate IWRS Manual.

The study blind should not be broken except in a medical emergency (where knowledge of the study drug received would affect the treatment of the emergency) or due to a regulatory requirement (for example for suspected unexpected serious adverse reactions). The blind will only be broken at the discretion of the Investigator, and if possible, following discussion on a case-by-case basis with the Sponsor/Medical Monitor. All calls resulting in an unblinding event will be recorded and reported by the IWRS to the Medical Monitor and the Sponsor.

In case of IWRS failure, a backup system is operated 24 hours every day of the year by the Sponsor enabling unblinding of treatment by calling the following universal toll free DBV Technologies numbers:

Germany and Ireland:	PPD
Canada and USA:	
Australia:	

If the blind is broken, the date, time, and reason must be recorded in the subject's source documents, in the e-CRF and any associated AE must be reported.

If an Investigator, site personnel performing assessments, or subject (parents/guardians), is unblinded, the subject must be listed as major protocol deviation and will be withdrawn from the study.

Serious unexpected suspected adverse reactions, which are subject to expedited reporting, will be unblinded by the Sponsor before submission to the Regulatory Authorities.

The overall randomization code will be broken only for reporting purposes. This will occur once all final clinical data have been entered into the database and all data queries have been resolved, the e-CRF has been signed and locked, and the assignment of subjects to the analysis sets has been completed.

### 5.5 Drug Accountability

The Investigator is responsible for maintaining accurate study drug accountability records throughout the study. Each site will have to complete a site study drug accountability log and an individual study drug accountability log for each subject. These records should include the amounts and dates that study drug supplies were received on-site, dispensed to the subject, returned by the subject, and returned to study drug distributor (or destroyed on-site, if applicable).

Each dispensing of study drug will be documented in the e-CRF via IWRS.

### 5.6 Compliance

It is the Investigators' responsibility to ensure that subjects (parents/guardians) are correctly instructed on how to store and administer the study drug. Records of study drug used and intervals between visits will be kept during the study. Drug accountability will be monitored by PAREXEL's site monitor during site monitoring visits and at the completion of the study. Subjects (parents/guardians) will be asked to return their unused study drug (boxes) when they come back for their study visits. All unused study drug (boxes) should be returned at the end of the study to the study drug distributor. The study drug should be dispensed by the Investigator, or by a qualified individual under the Investigator's supervision. An up-to-date treatment inventory/dispensing record must be maintained (see Section 5.5).

At each visit, prior to dispensing the study drug, previously dispensed study drug will be retrieved by the Investigator and compliance assessed. A global compliance of  $\geq 80\%$  over the whole treatment period is sought. Global compliance is defined as the total number of patches applied in the treatment period versus the number of days in that period of time. Compliance at each visit is to be calculated taking into account the total number of patches applied since the last visit versus the number of days in that period of time. Subjects exhibiting poor compliance (below 80%) at any specific time point during the treatment period should be counseled on the importance of good compliance to the study dosing regimen.

Subjects who are persistently non-compliant will be withdrawn from the study.

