### 4.3 Patient Withdrawal and Replacement

#### 4.3.1 *Criteria for Withdrawal from Study Treatment and Study*

Subjects may withdraw from the study including follow-up at any time without penalty and for any reason without prejudice to their future medical care.

Subjects must be withdrawn from the **study treatment** under the following circumstances:

- Pregnancy (see [Section 6.2.1.7](#));
- Severe “maculo-papular rash” or severe “dermatitis” failed to be controlled by adequate corrective treatments (including topical corticosteroids) and in spite of several study treatment interruptions;
- Severe anaphylaxis (or stage 3 anaphylaxis) (see [APPENDIX 5](#)) related to Viaskin® Peanut 250 µg patch application;
- More than 1 epinephrine injection for an AE related to Viaskin® Peanut 250 µg patch application (and not occurring during the DBPCFC).

If subjects are to withdraw due to pregnancy, the procedures that should be followed are described in [Section 6.2.1.7](#).

Subjects may be required to withdraw from the **study treatment or study** after discussion with the Sponsor and/or Investigator for the following reasons:

- AE(s);
- At the discretion of the Investigator, if she/he decides that it is in the subject’s best interest to be withdrawn from the study;
- The subject is unwilling to continue in the study (consent withdrawal);
- Lack of compliance with protocol requirements and procedures;
- The Sponsor, Regulatory Authorities, or Independent Ethics Committees (IECs)/Institutional Review Boards (IRBs) for any reason, stop the study;

- The subject fails to return to the clinic for scheduled visits and does not respond to telephone or written attempts at contact (lost to follow-up);
- Premature termination of the entire study as described in [Section 9.11](#).

In all cases, the primary reason for withdrawal, must be recorded in the e-CRF.

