#### **4.3.4 Data Collection and Follow-up after Withdrawal**

If a subject is prematurely withdrawn from the study drug for any reason before completing all study visits, the Investigator must make every effort to perform the evaluations described for the Early Termination Visit (see [Section 7.2.12](#)). The Investigator must furthermore complete all appropriate subject diary and e-CRF pages, providing the date and explanation for the subject's withdrawal/discontinuation. When indicated, the Investigator must arrange for appropriate follow-up and/or alternative medical care of the discontinued subject.

If the subject fails to attend a scheduled End of Study Visit, there will be at least 2 attempts to contact the subject's parents/guardians via telephone and written communication. If these receive no reply, the subject will be considered as lost to follow-up.

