### **7.2.12 Early Termination Visit**

Subjects who discontinue early from the study should, if possible, have an Early Termination Visit. This visit should take place as soon as possible after the subject stops taking the study drug (see also [Section 4.3](#)).

The following assessments will be performed at these visits:

- Physical examination (including a complete skin examination; see [Section 6.2.4](#));
- Vital signs (see [Section 6.2.3](#));
- Spirometry (FEV1) (see [Section 6.2.5](#));
- PEF (see [Section 6.2.6](#));
- SPT (see [Section 6.4.2](#));
- Pregnancy Test
- Immunological markers (see [Section 6.4.1](#));
- Laboratory tests ([Section 6.2.2](#));
- AEs recording (including volunteered or solicited AEs and AESI);
- Concomitant medications (see [Section 5.8](#));
- Check for any accidental peanut consumption (see [Section 6.4.4](#));
- Check subject diary;
- Check unused medication and assess medication compliance;
- Check skin reactions and grade severity (see [Table 6](#), [Section 6.2.8](#));
- Take a photograph of the sites of application of the Viaskin® patch and keep it in the subject's medical records or source documents.

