### 8.1.3.4 *Per-protocol Population*

The PP population will include all subjects from the ITT population who do not have major deviations from the protocol that may affect the primary efficacy endpoint (for instance, subjects who have not gone through the second DBPCFCs at Month 12, subjects with a global treatment compliance below 80%, etc.). The deviations to consider will be listed more exhaustively in the SAP. The PP population will be used to perform confirmatory analyses of the primary and secondary efficacy evaluations.

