##### 4.4.2 Intent-to-treat Population

The ITT population will be comprised of all subjects who are randomized. This population will be used to assess comparative efficacy information. Subjects will be analyzed according to the treatment they have been randomized to.

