### Main analysis

The primary efficacy endpoint is the difference between percentage of treatment responders in the active Viaskin® Peanut 250 µg group compared to the placebo group after 12 months of EPIT treatment. A subject is defined as a treatment responder if:

- The initial ED was  $\leq 10$  mg peanut protein (Screening ED subgroup 1) and the ED is  $\geq 300$  mg peanut protein at the Month 12 DBPCFC; or
- The initial ED was  $> 10$  mg peanut protein (Screening ED subgroup 2) and the ED is  $\geq 1,000$  mg peanut protein at the Month 12 DBPCFC.

The primary efficacy analysis will be performed on the ITT population, using missing=failure imputation method (which means that subjects with missing DBPCFC peanut eliciting dose value at M12 will be considered as non-responders).

The primary measure of treatment effect will be the difference in response rates between active and placebo treatment groups. The primary analysis will apply a Wald test at a 2-sided 5% significance level to evaluate a null hypothesis of no difference, and the corresponding 2-sided Newcombe 95% confidence interval (CI) for the difference in response rates will be calculated. The clinical relevance criterion for the primary analysis will be defined by a  $\geq 15\%$  lower confidence bound, and this condition will determine whether the primary objective has been successfully met.

The Wald test p-value will be calculated using the SAS® GENMOD procedure, with DIST=binomial and LINK=identity option of the MODEL statement.

The 2-sided Wilson 95% CIs of individual response rate will be presented overall and by treatment group using the SAS® FREQ procedure, with the RISKDIFF option.

All methods described above will be performed using SAS® procedures described in [Appendix 2: SAS® Code lines](#)

The study will be considered positive if the lower bound of the 95% CI of the difference between active treatment and placebo response rates is higher or equal to 15%. This 15% difference is intended to exhibit a clear robustness of the treatment effect.

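### Protocol 5.6 removes persistently non-compliant children from the study, at odds with 4.3.1, so Month 12 outcomes that could be measured become imputed failures

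*Protocol*

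**What the plan says.** **Non-compliance.** Protocol 5.6 seeks global compliance of at least 80%, asks for counselling when a child is below 80% at any time point, and ends: "Subjects who are persistently non-compliant will be withdrawn from the study". Protocol 4.3.1 lists "Lack of compliance with protocol requirements and procedures" among the reasons for which a subject may be required, after discussion, to leave either the study treatment or the study. Neither section defines persistent non-compliance.

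**Unblinding.** Protocol 5.4 says that if an investigator, assessing site staff or the family is unblinded, "the subject must be listed as major protocol deviation and will be withdrawn from the study". The lists in 4.3.1 do not mention unblinding.

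**After withdrawal.** Protocol 4.3.4 says "the Investigator must make every effort to perform the evaluations described for the Early Termination Visit". On timing, Protocol 7.2.12 adds: "This visit should take place as soon as possible after the subject stops taking the study drug". The assessments listed in 7.2.12 do not include a DBPCFC.

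**Analysis.** SAP 4.4.2: "The ITT population will be comprised of all subjects who are randomized". SAP 4.8.2, main analysis: "subjects with missing DBPCFC peanut eliciting dose value at M12 will be considered as non-responders". Low compliance has its own route: Protocol 8.1.3.4 and SAP 4.3.2 exclude from the per-protocol set "subjects with a global treatment compliance below 80" percent.

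**The concern.** Leaving treatment and leaving follow-up are different events, and only the second destroys the primary outcome. A child who has applied few patches can usually still be challenged at Month 12, and an analysis of all randomized subjects needs that result. Section 5.6 ends follow-up because of how the child took the treatment, and the analysis then records a failure that nobody observed.

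Three things are at stake. Missing data arise by rule in a pivotal trial. The primary result comes to depend partly on how each site reads an undefined word, which could differ between arms. And two sections of the protocol give sites different instructions for the same child.

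**Working it through.** **1. The chain in the text.** (a) 5.6 requires withdrawal from the study, not only from treatment. (b) The visit that follows has no challenge, so there is no Month 12 eliciting dose. (c) The child stays in the denominator and counts as a non-responder. (d) The sensitivity analyses in SAP 4.8.2 do not undo this. The FAS and per-protocol analyses leave the child out, and placebo-based multiple imputation and worst-case imputation fill in a value. None of them uses a measured outcome.

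**2. The SAP's own power.** Inputs from SAP 4.12 and 4.8.2: 220 active and 110 placebo; response 40% and 10%, both under missing=failure with at most 15% drop-out; success if the lower Newcombe 95% bound is at least 15%.

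Lower bound = (p1 − p2) − √[(p1 − L1)² + (U2 − p2)²], where L1 is the lower Wilson limit for active and U2 the upper Wilson limit for placebo. Power is the sum of the two binomial probabilities over all outcomes that meet the criterion.

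Result: 89.2%, against 90% in the SAP table (above 90% in its text). The figure reproduces to within about a point.

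**3. What rule-driven withdrawal could do.** The documents give no share of children affected; 5% of randomized is an assumption. The SAP rates imply completer rates of 0.40/0.85 = 47.1% and 0.10/0.85 = 11.8%.

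| Assumed 5% withdrawn under the rule | Active | Placebo | Difference | Power |
|---|---|---|---|---|
| Within the 15% allowance | 40.0% | 10.0% | 30.0 | 89.2% |
| Beyond it, both arms, would respond like completers | 37.6% | 9.4% | 28.2 | 81.9% |
| Beyond it, active only, would respond like completers | 37.6% | 10.0% | 27.6 | 77.4% |
| Beyond it, active only, would respond at 10% | 39.5% | 10.0% | 29.5 | 87.2% |
| Beyond it, both arms, would respond at 10% | 39.5% | 9.5% | 30.0 | 89.8% |
| Beyond it, placebo only, would respond like completers | 40.0% | 9.4% | 30.6 | 91.9% |

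Example, row 2: 47.1% × (0.85 − 0.05) = 37.6%, and 11.8% × 0.80 = 9.4%. On the same basis, 2% gives 86.6% and 10% gives 71.7%; the last requires a total loss of 25%.

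**4. What retention could gain.** Suppose the 5% lies inside the allowance and these children are challenged after all. If they respond like completers, the rates are 40 + 5 × 0.471 = 42.4% and 10 + 5 × 0.118 = 10.6%, and power is 94.0%. If the retained active children respond only at the placebo completer rate, the rates are 40.6% and 10.6%, the difference stays at 30.0 points, and power is 88.5%, slightly below the starting value.

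**The case against.** **The allowance already covers it.** The SAP's rates include up to 15% drop-out from any cause. In VIPES, 207 of 221 subjects completed (Protocol 1.1.1.2.3 and 1.1.1.2.4), a loss of 14/221 = 6.3%. Adding 5% gives 11.3%, still inside the allowance. This stands, and it removes any fixed power loss. A reader might calculate 5% × 40% = 2 points off the active rate and quote 79.6% power at 38% (84.9% at 39%). That holds only for loss beyond 15%, among children who would have responded at the full active rate despite poor compliance. The documents support neither condition.

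**The active arm need not be hit harder.** A reader might infer that it would, because VIPES reported local reactions in more than 90% of active subjects against 50% on placebo. But compliance counts patches, not hours (Protocol 5.6, SAP 4.7). A patch removed early for a reaction still counts, and the next one follows the next day (Protocol 5.2.1). The VIPES account also reports withdrawal for local reactions in only 2 of 221 subjects (0.9%), and Protocol 1.3 reports very good compliance. Longer interruptions could still differ by arm, but that is conjecture.

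**The ITT analysis is not partly per-protocol.** A per-protocol analysis drops non-compliers from the denominator; missing=failure keeps them as failures. Nor does the 80% exclusion contradict 5.6: a child may finish below 80% without having been withdrawn as persistently non-compliant.

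**Unblinded children differ.** Stopping a challenge rests on symptoms graded by the investigator (Protocol 6.1.1.3). A challenge read by staff who know the treatment could bias the primary comparison, so scoring such a child as a failure is defensible. This stands.

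The two compliance passages could also be read together, since 4.3.1 covers protocol non-compliance more broadly. But a site facing a persistently non-compliant child still finds *may* in one place and *will* in the other, and choosing between them decides whether the primary outcome is collected.

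**Conclusion.** The point holds as a design and wording defect. For persistently non-compliant children, 5.6 creates avoidable missing outcomes, the analysis turns them into failures, and 4.3.1 does not agree with it. This follows from the text and needs no numerical assumption.

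Its size cannot be fixed from the documents. With an assumed 5% affected, the effect on power runs from none, or a small gain, to about 12 points (89.2% to 77.4%). The larger losses require that the withdrawals exceed the 15% allowance and that these children would have responded like completers. The direction by arm is unknown: loss confined to placebo would raise the difference by 0.6 points. Nor is a power gain from retention established. The case for change is that outcomes should be measured rather than imputed, not that the trial is underpowered.

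**What to change.** Reconcile 5.6 with 4.3.1 and define *persistently*. State that non-compliance is a recorded deviation, handled through the existing per-protocol exclusion, and is not by itself a reason to leave study follow-up. The already scheduled Month 12 DBPCFC is attempted unless consent is withdrawn or the investigator judges it unsafe. Decisions about treatment itself are unchanged. Sections 4.3.4 and 7.2.12 need a matching sentence, so that an Early Termination Visit does not stand in for the Month 12 challenge in these children.

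For unblinding, ask only that 5.4 and 4.3.1 be reconciled. Any later challenge in an unblinded child would not be blind to treatment and should not enter the primary analysis as an ordinary outcome.

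The cost is protocol wording plus a few more of the challenges already planned. Some would be in children with little patch exposure, which may dilute the measured effect.

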### 5.7 Viaskin® Patch Adhesion

An evaluation of the Viaskin® patch adhesion will be conducted. The assessment of the patch adhesion to the skin will consist of a 28-day specific analysis to occur between Month 3 and Month 6 (whenever possible, these should be consecutive days). This assessment period can be extended up to Month 9 in case it has not been completed between Month 3 and Month 6 (see [Section 6.2.9](#)).

## 5.8 Prior and Concomitant Medication

Any medication the subject takes other than the study drug, including herbal and other non-traditional remedies, is considered as concomitant medication. Any medication used in the last 6 months or being administered at the time of screening is considered as prior medication.

At screening, subjects will be asked what medications they have been taking during the last 6 months. At each subsequent study visit, subjects will be asked what concomitant medications they are currently taking. All concomitant and prior medications must be recorded in the e-CRF.

The following information must be recorded in the e-CRF for each prior and concomitant medication: generic name, route of administration, start date, stop date, dosage, total daily dose, and indication. Any changes in the dosage or regimen of a concomitant medication must be recorded in the e-CRF.

Of note, prior or concomitant medication prescribed to a subject but not actually taken or administered should not be reported in the e-CRF, such as the epinephrine auto-injector prescribed for use in case of anaphylaxis but never injected intramuscularly.

### 5.8.1 Permitted Concomitant Medication

Application of a topical corticosteroid to treat any local condition (eczematous lesions, pruritus, edema, etc.) is allowed and should be recorded as concomitant medication. For local reactions to the Viaskin® patch, a topical medication (ointment, gel, cream) with 1% hydrocortisone or equivalent will be distributed to each randomized subject at discharge on Day 1. In case the 1% hydrocortisone topical medication is not sufficient to treat the local reaction, a topical medication containing a more potent corticosteroid can be prescribed and locally applied.

Oral antihistamines or oral corticosteroids are allowed to treat conditions determined as being allergic reactions and should be recorded as concomitant medications. These treatments should be limited in duration and stopped as soon as the condition has resolved. The Investigator will determine the best choice of treatment, the dose and the regimen according to the subject's age, and the type and the degree of severity of the reactions. Cetirizine is recommended as the oral antihistamine of choice.

Intramuscularly injectable epinephrine (EpiPen® or Twinject® or AnaPen®, or any other trade name available at the right dosage in the different countries) (auto-injector) will be distributed to each subject at discharge on Day 1 to be used in case of symptoms of anaphylaxis. The Investigator will explain to the subject/parents/guardians when and how to (self) inject the epinephrine according to the Anaphylaxis Emergency Action Plan which will also be given to the subject. The intramuscularly injectable epinephrine will be replaced if used or if it expires. Any use of injectable epinephrine should be recorded as a concomitant medication.

All other treatments prescribed by the Investigator or any other physician to treat any conditions are also permitted. Medications that are not noted in the [Section 5.8.2](#) are also permitted.

